3.5 Sample Size

Sample size

Based on pre-randomization data collected from January to December 2017, we estimate 5360 patients will be enrolled across 20 study sites over the 18-month enrolment period. Other study intervals ranging from 12 to 24 months are considered.

Justification

Original detectable effect size estimates: The study is based on the health center being the unit of randomization and aims to demonstrate the superiority of the intervention arm. The sample size calculation uses formulae appropriate for cluster-randomized trials with a parallel design and stratified and/or restricted randomization, including the addition of one extra cluster per arm to allow for the loss of degrees of freedom due to stratification to obtain conservative estimates.⁷ The original detectable effect size estimates were based on the outcome being the proportion of patients treated for microbiologically-confirmed TB within two weeks of referral for sputum-based testing. A type I error of 5% and power of 90% was assumed. Pre-randomization data collected from January to December 2017 from the 20 selected trial sites in Uganda suggested that the average proportion of patients referred for TB evaluation who initiate treatment for active TB within two weeks would be 6.7%, and the coefficient of variation (k) between clusters is 0.36, with a harmonic mean of 268 patients enrolled at each health center cluster during the 18-month enrolment period. Based on these assumptions and assuming a type I error of 5%, we will have 90% power to detect a 6% or greater absolute increase in the outcome proportion in the intervention arm (see **Table 1**). Table 1 also shows detectable absolute effect sizes with varying power (80%, 85%, 90%) during various trial time intervals and respective average cluster size estimates.

[figure not shown]

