Revised detectable effect size estimates: The revised detectable effect size estimates are for the outcome being the number of patients treated for microbiologically-confirmed TB within two weeks of referral for sputum-based testing. We first used 10 months of pre-intervention period data across all 20 clinics to assess 1) the geometric mean number of patients diagnosed and treated for TB within 14 days (new primary outcome), the natural log (ln) of the geometric mean and 3) the standard deviation of the natural log at control sites, intervention sites and overall. For the pre-intervention period, the intervention clinics have a lower geometric mean number of clinic attendees who were diagnosed with TB and started on TB treatment within 14 days compared with the control arm (table 2).

Table 2: summary data from the baseline period

	Geometric mean	Mean of ln outcome	SD of ln outcome
Control	14.70	2.69	0.23

Intervention	6.49	1.87	0.32
--------------	------	------	------

We then estimated the detectable effect size (expressed as a geometric mean ratio). The calculations assume the same parameters as for the original primary outcome (10 clinics/arm, 18-month trial duration to achieve geometric mean of 268 patients/cluster in control and intervention arms). Table 3 below shows the detectable effect size assuming within-arm SD of ln outcome of 0.2 to 0.3 and power of 80-90%. The detectable effect sizes shown below are conservative (calculations do not take into account the baseline differences between arms in the new primary outcome and are based on 10-months rather than full 24-months of pre-intervention data). Final calculations will be repeated once baseline data is fully entered and available for analysis.

Table 3: Detectable effect sizes

SD of ln outcome	Geometric Mean Ratio of the new primary outcome (intervention vs control)	
	80% power	90% power
0.2	1.30	1.36
0.3	1.49	1.58

We believe a GMR of 1.30-1.58 is a reasonable detectable effect size. Xpert MTB/RIF is twice as sensitive as smear microscopy (double the number of confirmed TB cases) and we expect onsite testing to reduce pre-treatment loss to follow-up by at least half (from 30% to <15%).

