4.4.3 Primary analysis of primary outcome

Analysis will be conducted at the cluster (clinic)-level. The outcome is the count of the number treated for microbiologically-confirmed TB within two weeks of referral for sputum-based testing at the clinic-level. Initially Poisson regression will be used, with an offset at the clinic level of the total number of days the clinic contributes individuals to the study (starting from 22 October 2018). Evidence for over-dispersion will be assessed and if over-dispersion is detected then negative binomial regression will be used, using the same offset. Either model will adjust for randomisation strata and the count of microbiologically-confirmed TB cases that initiated on treatment within 14 days in the 12 month period before 22 October 2018. The exact functional form of this covariate will be identified through fractional polynomials. Further adjustment for clinic-level factors that show imbalance will be explored, though the number of adjustment factors will be limited as all are at the clinic-level. See Annex tables 4a and 4b, and 5a.

Xpert Ultra cartridges will be used in our intervention (see Outcomes Definitions Section 3.4). Two sensitivity analyses will be performed reclassifying 1) all trace-positive results as negative and 2) trace-positive results in HIV negative patients as true positive (even if not confirmed by a second positive test) to determine the impact of Ultra on the primary outcome. We expect to see trace-positive results in between 10-20% of all positive Xpert Ultra results, irrespective of study arm. Therefore, sensitivity analyses will only be done if the ratio of trace-positive results to all positive Xpert Ultra results is similar in both trial arms.

No sub-group analyses for strata defined at the individual-level (e.g., sex and HIV status) will be conducted as the primary outcome analyses are conducted at the cluster-level.

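### The baseline gap between arms does not make Table 3 conservative: under the baseline-adjusted primary model this holds only if clinics' baseline and follow-up counts correlate above about 0.84

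*Combined protocol and SAP*

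**What the plan says.** In the amended SAP, section 3.5 gives detectable GMRs for the new count outcome in Table 3: 1.30 and 1.36 (SD of ln outcome 0.2; 80% and 90% power), 1.49 and 1.58 (SD 0.3). The stated inputs are "The calculations assume the same parameters as for the original primary outcome (10 clinics/arm, 18-month trial duration" and "assuming within-arm SD of ln outcome of 0.2 to 0.3 and power of 80-90" per cent. It then says: "The detectable effect sizes shown below are conservative (calculations do not take into account the baseline differences between arms in the new primary outcome". A second ground follows in the same sentence, that 10 rather than 24 months of pre-intervention data were used. The same sentence stands in SAP version 1.0 and in the amended protocol's Sample Size Considerations for Aim 1.

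Table 2 of the SAP reports the baseline geometric mean, mean ln and SD of ln by arm: "Control 14.70 2.69 0.23" and "Intervention 6.49 1.87 0.32".

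Section 4.4.3 defines the primary analysis as Poisson or negative binomial regression: "Either model will adjust for randomisation strata and the count of microbiologically-confirmed TB cases that initiated on treatment within 14 days", taken from the 12 months before 22 October 2018.

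For the original proportion outcome, section 3.5 describes its method as "including the addition of one extra cluster per arm to allow for the loss of degrees of freedom due to stratification".

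**The concern.** Calling a power calculation conservative because it leaves out a baseline imbalance makes sense only if including the imbalance would improve precision. Here it does the opposite. Once the baseline count is in the model, the arm effect is estimated from variation in arm that baseline does not explain. The further apart the arms are at baseline, the less of that variation remains. Adjustment does bring a gain, but the gain comes from the correlation between baseline and follow-up, which the documents do not report.

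Table 3 is the only power statement for the current primary outcome. If its margin runs the wrong way, readers will believe the trial could detect smaller effects than it can.

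**Working it through.** **Inputs.** All are from SAP 3.5 unless noted: 10 clusters per arm; type I error 5% (taken as two-sided, which the SAP does not state); SD of ln outcome 0.2 and 0.3; baseline mean ln 2.69 and 1.87; baseline SDs 0.23 and 0.32. Section 4.1 gives 63,504 possible allocations, which is 252^2, so each stratum has five clusters per arm and stratum is balanced over arm.

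**1. Reproduce Table 3.** GMR = exp[(1.960 + z_power) x SD x sqrt(2/n)].

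| n per arm | SD 0.2, 80% | SD 0.2, 90% | SD 0.3, 80% | SD 0.3, 90% |
|---|---|---|---|---|
| Stated | 1.30 | 1.36 | 1.49 | 1.58 |
| 10 | 1.285 | 1.336 | 1.456 | 1.545 |
| 9 | 1.302 | 1.357 | 1.486 | 1.582 |
| 8 | 1.323 | 1.383 | 1.522 | 1.626 |

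Table 3 fits n = 9. A t-test with 10 per arm and 18 df fits equally well (1.303, 1.359, 1.488, 1.584). Either way it is an unadjusted comparison with no baseline covariate.

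**2. Imbalance factor.** In a linear model on the log scale, Var(adjusted effect) = SD^2 x (1 - rho^2) x [2/10 + gap^2/Sxx].

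- Gap = 2.69 - 1.87 = 0.82.
- Sxx = 9 x (0.23^2 + 0.32^2) = 1.398.
- gap^2/Sxx = 0.6724/1.398 = 0.481, against 2/10 = 0.200.
- Factor = (0.200 + 0.481)/0.200 = 3.41, the same as 1/(1 - R2) with R2 = 0.706 from regressing ln baseline on arm.

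**3. Net effect on Table 3.** Variance ratio = 3.41 x (1 - rho^2). Break-even is at rho^2 = 0.706, so rho = 0.84. The 90%-power GMRs use n = 9 with SD multiplied by the square root of the ratio.

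| rho | Variance ratio | GMR, SD 0.2 (stated 1.36) | GMR, SD 0.3 (stated 1.58) | Power at the stated GMR |
|---|---|---|---|---|
| 0 | 3.41 | 1.76 | 2.33 | about 42% |
| 0.5 | 2.55 | 1.63 | 2.08 | about 53% |
| 0.7 | 1.74 | 1.50 | 1.83 | about 70% |
| 0.84 | 1.00 | 1.36 | 1.58 | about 90% |
| 0.9 | 0.65 | 1.28 | 1.45 | about 98% |

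Simulating the linear model with arm, stratum and baseline (16 df) gives similar ratios: about 3.5-3.7, 2.5-2.8, 1.8, 1.0 and 0.7.

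**4. Which rho is plausible?** Assume the true between-clinic SD of ln rate is 0.3, the top of Table 3's range, and perfectly stable over time. Scale the 10-month geometric means to the 12-month covariate and the 18-month outcome: 17.64 and 26.46 at control counts, 7.79 and 11.68 at intervention counts. With Poisson noise only, rho = 0.09/sqrt[(0.09 + 1/m12)(0.09 + 1/m18)].

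- Control counts: 0.09/sqrt(0.1467 x 0.1278) = 0.66.
- Intervention counts: 0.09/sqrt(0.2184 x 0.1756) = 0.46.

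Reaching 0.84 needs a true SD of about 0.50 at control counts and about 0.75 at intervention counts, far above Table 3's range.

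**5. Check Table 2.** Pure Poisson noise at 14.70 and 6.49 gives SDs of ln of about 1/sqrt(14.70) = 0.26 and 1/sqrt(6.49) = 0.39. The reported 0.23 and 0.32 are smaller, before any real variation between clinics. If they change, the factor changes: a common SD of 0.4, 0.5 or 0.7 gives 2.17, 1.75 or 1.38 (break-even rho 0.73, 0.65, 0.53). If the printed figures were standard errors (an assumption; SDs about 0.73 and 1.01), the factor is 1.24 and break-even 0.44. With that pooled SD of 0.88, however, the unadjusted 90%-power GMR would be about 3.8.

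**6. Stratification cluster.** The usual cluster-trial formula for proportions with 6.7%, k = 0.36, 268 per cluster and 90% power gives 6.94% with n = 8 and 6.34% with n = 9. Table 1 prints 6.9%, so it uses 10 - 2 clusters. Table 3 does not; charging the cluster gives the n = 8 row in step 1: 1.32, 1.38, 1.52, 1.63.

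**The case against.** A reader might infer that the gap simply triples the variance and so makes Table 3 optimistic. The documents do not support that. The factor of 3.4 is the penalty before the gain from adjustment; the net variance more than triples only if rho is below about 0.35, and above 0.84 Table 3 remains conservative. No rho is given, so the direction is not settled by the documents alone. The Poisson bound in step 4 points one way, but it is conditional on Table 3's SD range.

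There is also a tension in the inputs: the same Table 2 SDs that give 3.4 look too small to be SDs of ln counts. That stands. It makes the size provisional, but it does not restore the baseline gap as a safety margin, because at any fixed rho the gap still only adds variance.

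The second ground for conservatism, the short baseline window, is not refuted here. Longer accrual does reduce count noise. It is a separate argument and needs its own figures.

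A reader might also infer that a null result would be taken to exclude GMRs of 1.3 to 1.6. Section 4.4.1 promises 95% confidence intervals, and exclusion is read from those. The clusters are already randomised, so no design decision turns on this, and section 3.5 already promises to repeat the calculation. It does not say that the repeat will reflect the adjusted model.

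On the stratification cluster, the 18-df t-test fits Table 3 as well as a deduction of one cluster does. Under either reading the loss for stratification is not charged. The effect is small.

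**Conclusion.** The concern holds in conditional form. The baseline gap is not a valid reason to call Table 3 conservative, because the primary model adjusts for the baseline count. At Table 2's figures the claim is true on this ground only if rho exceeds about 0.84. If the true between-clinic SD is at most 0.3, Poisson noise holds rho to about 0.46-0.66, and the 1.58 cell would then be nearer 1.9 to 2.1.

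This rests on a linear log-scale approximation to the Poisson or negative binomial model, a log-form covariate (section 4.4.3 leaves the form to fractional polynomials), two-sided 5% testing, the 10-month gap standing in for the 12-month covariate, and Table 2's SDs as printed. The last is the weakest. The missing stratification cluster is a separate, smaller fault that does not depend on rho.

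**What to change.** - Remove the baseline difference as a ground for conservatism in SAP 3.5 and in the protocol's Sample Size Considerations. If the 10-month ground is kept, support it with figures.
- In the recalculation already promised, first verify the Table 2 SDs against the clinic counts.
- From the pre-trial registers, estimate R2 (ln baseline count on arm) and rho (within-arm correlation between an earlier and a later period). Multiply the variance by (1 - rho^2)/(1 - R2), deduct the stratification cluster, and restate the detectable GMR with the rho used.

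The cost is a wording change and a short calculation on data already being collected. The downside is that the stated detectable effect is likely to become less favourable.

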3.6 Blinding

The trial will be open-label for participants and researchers, as blinding of the assigned intervention is not feasible given intervention implementation at the health center level. Staff, however, will be blinded to the intervention allocations through the use of codes to identify clusters rather than health center names. Where possible, the investigators and study staff will be masked to ongoing aggregated data by study. The trial statistician and data manager will have access to the aggregate data. Some site-level data will be used for performance feedback to sites in the intervention arm; this data will not be a comparison to baseline sites across study arms.

4. Randomization

4.1 Sequence Generation

A random allocation sequence will be generated by STATA 14 (StataCorp LP, College Station, TX). Randomisation of clusters to the intervention or control arm was conducted using stratification and restriction. Stratified randomisation was used to help reduce between-cluster variability and achieve balance at baseline. Using data from 2017 on the percentage of adult clinic attendees being investigated for TB who started TB treatment within 14 days, the clusters were stratified into two equal-sized groups – “low” and “high” percentages of this outcome based on the median. Restricted randomisation was used to help ensure balance for key factors. Variables we restricted on were; year cluster enrolled in project (2017 vs. 2018); sputum transport frequency to Xpert hub; distance to Xpert hub; number of patients evaluated for TB; percentage starting TB treatment within 14 days; urban vs. rural health clinics; HIV prevalence; number of facilities per district. For these restriction criteria the overall proportion of unacceptable allocations was calculated and the the validity assessed using the validity matrix.⁹ From a total of 63,504 possible randomisations based on two equal-sized strata, applying the restriction criteria resulted in 11,392 randomisations; one of these was chosen at random.

4.2 Allocation concealment mechanism

Allocation concealment was used to prevent selection bias by concealing from the research staff the allocation sequence until assignment had occurred.

4.3 Implementation

The trial statistician generated the random allocation assignments, and clusters were enrolled by local study staff. Eligible individual patients will be included in clusters through complete enumeration. District health officers provide administrative authority and consent to health center participation prior to randomization. Consent is documented in a signed Memorandum of Understanding (MOU) between the district and the National Tuberculosis and Leprosy Control Program (NTLP), endorsed by the Chief Administrative Officer, the District Health Officer, and the Program Manager for NTLP. A copy of the agreement is provided to the facility in-charge at each health center.

A public ceremony for randomization was held in Kampala, Uganda. Facility in-charges, district health officers, and representatives from NTLP attended.

4.4 Statistical Methods

4.4.1 General analyses principles

We will calculate and compare all effectiveness outcomes for the two trial arms using prespecified analyses following the intention-to-treat principle. Statistical analysis methods to determine intervention effect on outcomes will be used that are appropriate for CRTs with a small number of clusters. Analysis of cluster-level summaries is based on a total of 20 clusters (10 per arm), each comprised of one health center, and each being given equal weight. Effect estimates will be reported with 95% confidence intervals, and an associated P-value.

4.4.2 Baseline data

Baseline variables (from the 12 month period before 22 October 2018 and socio-demographic data from 12 month period after 22 October 2018) will be cross-tabulated to check for appropriate balance between study arms and to characterize the study population using summary statistics both at cluster and individual levels (Annex **Table 1, 2**).

Cluster (*i.e.* health center) level data will be collapsed across study arms and compared using mean, median and range with standard deviations and/or interquartile ranges as appropriate. The basis of this analysis will be data on demographics, health center and laboratory infrastructure, organizational hierarchy, Xpert referral network, and TB testing and treatment collected during site assessment, recruitment, and guidelines training.

Individual level data for all patients eligible for analysis will also be collapsed across study arms and compared using mean, median and range with standard deviations and/or interquartile ranges as appropriate. These individual factors include age, sex, HIV status, and ART status.

We will summarize data obtained during the pre-randomization period for the cohort of health centers and patients who are being enrolled in the study and randomized to a trial arm (Annex table 1).

We will also summarise of numbers referred for TB testing in intervention and control arms (collapsed over cluster) in the 12 month period after 22 October 2018 (Annex Table 3).

Descriptive data between control and intervention arms will be presented in tabular format in lieu of formal statistical comparison or significance tests, and will be reviewed to confirm comparability and identify any substantial imbalances. Adjusted effect estimates will be calculated by study arm to account for imbalance of covariates which are risk factors for the outcome of interest. Losses in degrees of freedom due to cluster-level covariate adjustments will be accounted for in all calculations.

4.4.3 Primary analysis of primary outcome

Analysis will be conducted at the cluster (clinic)-level. The outcome is the count of the number treated for microbiologically-confirmed TB within two weeks of referral for sputum-based testing at the clinic-level. Initially Poisson regression will be used, with an offset at the clinic level of the total number of days the clinic contributes individuals to the study (starting from 22 October 2018). Evidence for over-dispersion will be assessed and if over-dispersion is detected then negative binomial regression will be used, using the same offset. Either model will adjust for randomisation strata and the count of microbiologically-confirmed TB cases that initiated on treatment within 14 days in the 12 month period before 22 October 2018. The exact functional form of this covariate will be identified through fractional polynomials. Further adjustment for clinic-level factors that show imbalance will be explored, though the number of adjustment factors will be limited as all are at the clinic-level. See Annex tables 4a and 4b, and 5a.

Xpert Ultra cartridges will be used in our intervention (see Outcomes Definitions Section 3.4). Two sensitivity analyses will be performed reclassifying 1) all trace-positive results as negative and 2) trace-positive results in HIV negative patients as true positive (even if not confirmed by a second positive test) to determine the impact of Ultra on the primary outcome. We expect to see trace-positive results in between 10-20% of all positive Xpert Ultra results, irrespective of study arm. Therefore, sensitivity analyses will only be done if the ratio of trace-positive results to all positive Xpert Ultra results is similar in both trial arms.

No sub-group analyses for strata defined at the individual-level (e.g., sex and HIV status) will be conducted as the primary outcome analyses are conducted at the cluster-level.

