The minimum detectable effect size is based on published literature, our preliminary data demonstrating the increased sensitivity of Xpert Ultra vs. smear microscopy (95% vs. 40%), and reduced pre-treatment loss to follow-up expected in the intervention vs. control arms due to rapid, onsite molecular testing (7% vs. 30%). When applying these parameters to a population of 1000 individuals with TB prevalence of 10%, we would expect 95 patients to be diagnosed with TB and 88 to start treatment within 14 days in the intervention arm, and 40 patients to be diagnosed with TB and 28 to start treatment within 14 days in the control arm. Thus, the expected difference in the primary outcome proportion would be 8.8% vs. 2.8%, or 6%.⁸

Table 1. Absolute difference in the proportion of clinic attendees initiating TB treatment within 14 days of initial sputum submission, among those referred for TB testing

Average cluster size	Effect size (10 clusters per arm, $k=0.36$)		
	80% Power	85% Power	90% Power

178 (12 months)	5.9%	6.5%	7.4%
223 (15 months)	5.7%	6.3%	7.1%
268 (18 months)	5.5%	6.1%	6.9%
312 (21 months)	5.4%	6.0%	6.7%
357 (24 months)	5.3%	5.9%	6.6%

Figure 1. Effect size by cluster size. Number of clusters per arm is 10, $k=0.36$.

The primary outcome was changed to a count of the number of adults diagnosed and treated with TB at the cluster-level. The new primary outcome better reflects the intended effect of the multi-component intervention to drive more people who present to health facilities through the entire TB diagnostic evaluation cascade of care, including being screened for TB, tested for TB (if screen-positive), diagnosed with TB (if tested) and initiated on treatment (if diagnosed). Process re-design is expected to help improve the number screened and tested. Onsite molecular testing is expected to increase the numbers diagnosed (increased sensitivity) and treated (faster turn-around time and reduced workload). Performance feedback is expected to maintain improvement along each step of the cascade. Thus, the intervention is expected to increase both the number of patients entering and completing the cascade of care.

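### Section 4.4.3 sets no over-dispersion rule, standard error or reference distribution for the primary count model on 20 clinics, and t on 16 df alone would not hold 5% if clinics are over-dispersed

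*Combined protocol and SAP*

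**What the plan says.** Under the amended SAP, Section 4.4.3, the primary outcome is a count per clinic. It is modelled by Poisson regression with days of contribution as offset, adjusted for randomisation stratum and for the same count in the 12 months before 22 October 2018. Two parts of the model are decided from the data. On the distribution: "Evidence for over-dispersion will be assessed and if over-dispersion is detected then negative binomial regression will be used, using the same offset". On the baseline count: "The exact functional form of this covariate will be identified through fractional polynomials". The section adds that further clinic-level adjustment will be kept limited.

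Two general statements bear on inference. Section 4.4.1: "Statistical analysis methods to determine intervention effect on outcomes will be used that are appropriate for CRTs with a small number of clusters". Section 4.4.2: "Losses in degrees of freedom due to cluster-level covariate adjustments will be accounted for in all calculations".

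For proportions, Section 4.4.4.2 names both the variance source (the residual mean square from an ANOVA of stratum, arm and their interaction) and the reference distribution (t, 16 df). Section 4.4.3 names neither for the primary count, and Section 4.4.4.1 applies the same approach to all secondary counts.

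**The concern.** With 20 observations and four coefficients (intercept, arm, stratum, baseline), small-sample inference depends on choices that Section 4.4.3 leaves open: how over-dispersion is judged, which standard error is used, z or t, and how far the fractional polynomial search may go. The general promises do not say how they apply to a likelihood model.

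This is more than missing detail. The procedure as written, a pre-test followed by maximum-likelihood negative binomial, has two weaknesses that a t critical value does not remove. The pre-test often stays with Poisson when modest over-dispersion is present, and the maximum-likelihood dispersion is biased low with 20 points. At stake are the size of the primary test and the coverage of its 95% interval.

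**Working it through.** **1. The plan's own figure.** Section 3.5 states: "Table 3 below shows the detectable effect size assuming within-arm SD of ln outcome of 0.2 to 0.3 and power of 80-90" percent. With 10 clinics per arm less one for stratification, the detectable ratio is exp[(z0.975 + z_power) × SD × √(2/9)]. SD 0.2 gives 1.302 (80% power) and 1.357 (90%); SD 0.3 gives 1.486 and 1.582. Table 3 prints 1.30, 1.36, 1.49 and 1.58, so it reproduces. Planning therefore allowed for few clusters; Section 4.4.3 does not say how the analysis will.

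**2. Event counts.** The 10-month geometric means are 14.70 and 6.49, and √(14.70 × 6.49) = 9.77. Scaled to time, this is 11.7 baseline events (12 months) and 17.6 trial events (18 months) per clinic. The original planning figures agree: 178 × 6.7% = 11.9 and 268 × 6.7% = 18.0.

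**3. How much over-dispersion?** The documents do not settle this.
- Section 3.5 gives, for the original proportion outcome, "the coefficient of variation (k) between clusters is 0.36, with a harmonic mean of 268 patients enrolled at each health center cluster". If k is the true between-clinic CV, the log SD is √ln(1 + 0.36²) = 0.35. If it still contains sampling noise, k² less noise is 0.1296 − 0.933/11.9 = 0.051, and the log SD is 0.22.
- Table 2's within-arm SDs of ln count are 0.23 and 0.32. Approximate Poisson noise is 1/√14.70 = 0.26 and 1/√6.49 = 0.39. These SDs show no over-dispersion.
- Table 2 also shows that "the intervention clinics have a lower geometric mean number of clinic attendees who were diagnosed with TB", a log gap of 2.69 − 1.87 = 0.82. Under Poisson noise alone with a common mean of 9.77, its SE is √(2/(10 × 9.77)) = 0.143, so the gap is 5.7 SEs. Against the table's own SDs, its SE is √((0.23² + 0.32²)/10) = 0.125, so it is 6.6 SEs. Those SDs and that gap sit badly together, and the table is weak ground for any single value.

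The settings 0, 0.13, 0.25 and 0.37 below are assumptions spanning none to substantial.

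**4. Check by hand.** Under strong over-dispersion the negative binomial fit behaves like a log-scale regression with variance divided by 20 instead of 16. With z the null rejection is 2P(t16 > 1.96 × √(16/20)) = 9.9%. With the t16 critical value 2.120 it is 2P(t16 > 1.896) = 7.6%. One more fitted parameter under z gives 11.0%.

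**5. Null simulation.** Each run has 20 clinics, two strata of 10, five per arm per stratum and equal days, with 8,000 runs per setting (Monte Carlo SE 0.2-0.4 points). Assumptions not in the documents: two-sided 5%, likelihood-ratio pre-test at 5% unless stated, baseline-trial correlation of log rates 0.8 (0.5-1.0 at log SD 0.37), and first-degree fractional polynomial (FP1) chosen by best fit.

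| Rejection, % | log SD 0 | 0.13 | 0.25 | 0.37 |
|---|---|---|---|---|
| Switch, t16, log baseline | 3.2 | 5.6 | 8.3 | 8.6-9.0 |
| Switch, t16, best-fit FP1 | 3.5 | 5.9 | 9.3 | 10.5-10.6 |
| Switch, t16, Pearson pre-test, log baseline | 3.3 | 5.2 | 7.1 | 8.2 |
| Switch, Wald z, log baseline | 4.7 | 7.6 | 10.9 | 11.2-11.5 |
| Switch, Wald z, best-fit FP1 | 5.1 | 8.0 | 12.1 | 13.1-13.4 |
| Poisson, Pearson-scaled (≥1), t16 | 2.6 | 3.8 | 4.3 | 4.8-5.2 |
| Regression of log counts, t16 | 4.7 | 4.8 | 4.6 | 4.6-5.1 |

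**6. Variations.** In k-based runs (4,000-8,000 per setting), strata were formed by a median split on the 2017 percentage. The t16 switch with log baseline gives 8.4-9.2% at log SD 0.22 and 7.6-9.9% at 0.35; with FP1, 9.0-11.5% and 9.9-11.7%. A proxy for the restricted randomisation at 0.35 gives 7.4-9.1% and 9.5-10.8%. A separate 3,000-run simulation gives t16 rates of 3.3, 5.5, 7.1, 7.8 and 9.3% at 0, 0.13, 0.22, 0.25 and 0.35. The unstated detection rule matters by itself: switching whenever Pearson chi-square/df exceeds 1 rejects up to about 3 points less often than the likelihood-ratio rule. Across independent runs under over-dispersion, the scaled Poisson stayed at 3.7-5.9%.

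**7. Away from the null.** Section 3.5 says "we would expect 95 patients to be diagnosed with TB and 88 to start treatment within 14 days in the intervention arm", against 28 in control, a ratio of 88/28 = 3.14. At that ratio every method rejected in all runs. Wald interval coverage over ratios 1.30, 1.58 and 3.14 was 91-92% at log SD 0.13 and 88-91% at 0.25-0.37 with a log baseline (86-92% with FP1). For the t16 switch, coverage at a ratio of 1 is 100% less the null rejection, for example 100 − 8.3 = 91.7% at 0.25.

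**The case against.** The strongest reply is that the SAP never chooses Wald z. Section 4.4.2 extends df accounting to every calculation, which on its face includes the primary model, and Section 4.4.3 itself limits adjustment factors. A reader might infer from the Wald rows that the trial's error rate is 7-14%. The documents do not support that: z is not specified, and the df promise speaks against it. This objection stands, so the t16 rows carry the point. It does not dispose of it, because t16 on the same switch still exceeds 5% at moderate over-dispersion.

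The second reply is that over-dispersion is unproven. This also stands in part. Table 2's within-arm SDs are at or below Poisson noise, k describes a proportion and not the count, and the detection rule, the correlation and best-fit FP1 are assumptions. With no extra variation the test is valid or slightly conservative.

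Third, a reader might infer that a positive result would be in doubt. At the anticipated effect it would not be. Nor would counting trials that are significant under one method but not another measure the harm: at a true non-null ratio those rejections are correct, and the count mixes error inflation with loss of power.

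**Conclusion.** The gap in the text is certain; its size is conditional. If the df promise is honoured in the simplest way, null rejection is about 3% with no extra-Poisson variation, 5-6% at a clinic log SD of 0.13, and about 7-9% at 0.22-0.37 with a log baseline, or up to about 10-12% with best-fit FP1. Wald z, neither specified nor excluded by name, would give about 5%, 7-8% and 9-12% (up to about 14% with FP1). The rates level off and do not climb steadily.

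The significance call is at stake only for true effects near Table 3's ratios of 1.30-1.58. The interval would be too narrow at any effect size if clinics are over-dispersed. Secondary counts inherit the problem, mainly the commoner ones: at log SD 0.37 the Wald switch rejected 8.7% at 3 events per clinic and 5.4% at 1. This should be fixed; confidence in its size is medium.

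**What to change.** In Sections 4.4.3 and 4.4.4.1:
- Drop the Poisson/negative binomial pre-test for the primary inference. Use Poisson with the same offset, a Pearson-scaled standard error (scale at least 1) and t on the residual df. That is 16 with arm, stratum and one baseline term, and one fewer per further clinic-level factor. For the strata-only ratio in Annex Table 5a, state the choice: 17 df without the stratum-by-arm interaction, or 16 with it as in Section 4.4.4.2.
- Fix the baseline term in advance, for example ln(count + 0.5). Keep the fractional polynomial form and the negative binomial fit as sensitivity analyses.
- An acceptable alternative is cluster-level regression of ln((count + 0.5)/days) with t on 16 df. It reports a geometric mean ratio, the scale of Table 3, but adding 0.5 suits sparse counts less well.

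A permutation test over the 11,392 acceptable allocations is possible, but it needs its own interval construction and was not tested on that set.

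The cost is wording and a few lines of code. Intervals are about 1.1-1.4 times as wide as Wald, and the test is slightly conservative (about 2.6-3%) if there is no over-dispersion. Apparent power at a ratio of 1.58 falls from 94% to 87% at log SD 0.25 and from 84% to 74% at 0.37 relative to Wald, partly because the Wald figure is inflated. There is no loss at a ratio of 3.1.
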